3.2.3 Exploratory Objective Estimands

Table 4 Exploratory Objective Estimands

Objective 1	MQoL at 24 hours postdose during the DBT Phase
Outcome Research Endpoint	Mean total and domain scores at 24 hours postdose during the DBT Phase
Summary	Values using descriptive statistics at 24 hours postdose by treatment group during the DBT Phase for the DBT efficacy analysis set
Intercurrent Events	Rescue medication use: treatment policy strategy Nonrescue acute headache medication use: treatment policy strategy Prophylactic migraine medication use: treatment policy strategy Study drug discontinuation: treatment policy strategy
Objective 2	MQoL at 24 hours postdose after each of the first 5 qualifying migraine attacks during the OLE Phase
Outcome Research Endpoint	Mean total and domain scores at 24 hours postdose for each of the first 5 EQMAs ≥ 23 hours apart, reported separately, in the OLE Phase
Summary	Values using descriptive statistics at 24 hours postdose after each of the first 5 EQMAs ≥ 23 hours apart in the OLE Phase by treatment group and overall for the OLE efficacy analysis set
Intercurrent Events	Rescue medication use: treatment policy strategy Nonrescue acute headache medication use: treatment policy strategy Prophylactic migraine medication use: treatment policy strategy Study drug discontinuation: treatment policy strategy
Objective 3	Migraine headache pain relief at all scheduled time points postdose during the DBT Phase
Efficacy Endpoint	Percentage of subjects with migraine headache pain intensity of none or mild at each time point postdose (15, 30, 45, 60, 90 min and 2, 3, 4, 6, 8, 24, 48 hours) during the DBT Phase. Migraine headache pain intensity is measured on a 4-point numeric rating scale (0=none, 1=mild, 2=moderate, 3=severe)
Summary	Percentage of subjects achieving the endpoint response criteria by treatment group and difference in percentages between treatment groups using Mantel-Haenszel risk estimation for the DBT efficacy analysis set
Intercurrent Events	Rescue medication use: composite strategy Nonrescue acute headache medication use: treatment policy strategy Prophylactic migraine medication use: treatment policy strategy Study drug discontinuation: not applicable (single dose)
Objective 4	Migraine headache pain freedom at all scheduled time points postdose during the DBT Phase
Efficacy Endpoint	Percentage of subjects with migraine headache pain intensity of none at each time point postdose (15, 30, 45, 60, 90 min and 2, 3, 4, 6, 8, 24, 48 hours) during the DBT Phase. Migraine headache pain intensity is measured on a 4-point numeric rating scale (0=none, 1=mild, 2=moderate, 3=severe)

Summary	Percentage of subjects achieving the endpoint response criteria by treatment group and difference in percentages between treatment groups using Mantel-Haenszel risk estimation for the DBT efficacy analysis set
Intercurrent Events	Rescue medication use: composite strategy Nonrescue acute headache medication use: treatment policy strategy Prophylactic migraine medication use: treatment policy strategy Study drug discontinuation: not applicable (single dose)
Objective 5	MBS freedom at all scheduled time points postdose during the DBT Phase
Efficacy Endpoint	Percentage of subjects with MBS reported on study before dosing but absent at each time point postdose (15, 30, 45, 60, 90 min and 2, 3, 4, 6, 8, 24, 48 hours) during the DBT Phase
Summary	Percentage of subjects achieving the endpoint response criteria by treatment group and difference in percentages between treatment groups using Mantel-Haenszel risk estimation for the DBT efficacy analysis set
Intercurrent event	Rescue medication use: composite strategy Nonrescue acute headache medication use: treatment policy strategy Prophylactic migraine medication use: treatment policy strategy Study drug discontinuation: not applicable (single dose)
Objective 6	Return to normal function at all scheduled time points postdose during the DBT Phase
Efficacy Endpoint	Percentage of subjects with a functional disability level of normal at each time point postdose (15, 30, 45, 60, 90 min and 2, 3, 4, 6, 8, 24, 48 hours) during the DBT Phase; evaluated for the subset with functional disability at the time of dosing. Functional disability level is measured on a 4-point numeric rating scale (0=normal, 1=mildly impaired, 2=severely impaired, 3=requires bedrest), and functional disability are defined as mildly impaired, severely impaired, or requires bedrest
Summary	Percentage of subjects achieving the endpoint response criteria by treatment group and difference in percentages between treatment groups using Mantel-Haenszel risk estimation for the DBT efficacy analysis set with functional disability at the time of DB study drug dosing
Intercurrent event	Rescue medication use: composite strategy Nonrescue acute headache medication use: treatment policy strategy Prophylactic migraine medication use: treatment policy strategy Study drug discontinuation: not applicable (single dose)
Objective 7	Photophobia freedom at all scheduled time points postdose during the DBT Phase
Efficacy objective	Percentage of subjects with photophobia absent at each time point postdose (15, 30, 45, 60, 90 min and 2, 3, 4, 6, 8, 24, 48 hours) during the DBT Phase; evaluated for the subset with photophobia present at the time of dosing
Summary	Percentage of subjects achieving the endpoint response criteria by treatment group, and difference in percentages between treatment groups using Mantel-Haenszel risk estimation for the DBT efficacy analysis set with photophobia present at the time of DB study drug dosing
Intercurrent Events	Rescue medication use: composite strategy Nonrescue acute headache medication use: treatment policy strategy

	Prophylactic migraine medication use: treatment policy strategy Study drug discontinuation: not applicable (single dose)
Objective 8	Phonophobia freedom at all scheduled time points postdose during the DBT Phase
Efficacy Endpoint	Percentage of subjects with phonophobia absent at each time point postdose (15, 30, 45, 60, 90 min and 2, 3, 4, 6, 8, 24, 48 hours) during the DBT Phase; evaluated for the subset with phonophobia present at the time of dosing
Summary	Percentage of subjects achieving the endpoint response criteria by treatment group and difference in percentages between treatment groups using Mantel-Haenszel risk estimation for the DBT efficacy analysis set with phonophobia present at the time of DB study drug dosing
Intercurrent Events	Rescue medication use: composite strategy Nonrescue acute headache medication use: treatment policy strategy Prophylactic migraine medication use: treatment policy strategy Study drug discontinuation: not applicable (single dose)
Objective 9	Nausea freedom at all scheduled time points postdose during the DBT Phase
Efficacy Endpoint	Percentage of subjects with nausea absent at each time point postdose (15, 30, 45, 60, 90 min and 2, 3, 4, 6, 8, 24, 48 hours) during the DBT Phase; evaluated for the subset with nausea present at the time of dosing
Summary	Percentage of subjects achieving the endpoint response criteria by treatment group and difference in percentages between treatment groups using Mantel-Haenszel risk estimation for the DBT efficacy analysis set with nausea present at the time of DB study drug dosing
Intercurrent Events	Rescue medication use: composite strategy Nonrescue acute headache medication use: treatment policy strategy Prophylactic migraine medication use: treatment policy strategy Study drug discontinuation: not applicable (single dose)
Objective 10	Pain relapse from 2 to 48 hours post dose during the DBT Phase
Efficacy Endpoint	Percentage of subjects with migraine headache pain intensity of mild, moderate, or severe at any time point after 2 hours postdose during the DBT Phase; evaluated for the subset with pain freedom at 2 hours postdose during the DBT Phase
Summary	Percentage of subjects achieving the endpoint failure criteria by treatment group and difference in percentages between treatment groups using Mantel-Haenszel risk estimation for the DBT efficacy analysis set with pain freedom at 2 hours postdose during the DBT Phase
Intercurrent Events	Rescue medication use: composite strategy Nonrescue acute headache medication use: treatment policy strategy Prophylactic migraine medication use: treatment policy strategy Study drug discontinuation: not applicable (single dose)
Objective 11	Time to migraine headache pain relief through 48 hours postdose during the DBT Phase
Efficacy Endpoint	Time to first migraine headache pain relief (defined as headache pain intensity of none or mild) through 48 hours postdose during the DBT phase

Summary	Descriptive statistics by treatment group, and by randomization stratum within treatment group: (1) estimated median (hours) with measures of variance; and (2) Kaplan-Meier estimated cumulative probabilities through 48 hours
Intercurrent Events	Rescue medication use: composite strategy Nonrescue acute headache medication use: treatment policy strategy Prophylactic migraine medication use: treatment policy strategy Study drug discontinuation: not applicable (single dose)
Objective 12	Mean number of acute migraine medication days per month in each month and over the entire OLE Phase
Efficacy Endpoint	Mean number of acute migraine medication days per month in each month (defined as 4-week interval), and over the entire OLE Phase (Weeks 1 to 12)
Summary	Values by treatment group and overall using descriptive statistics for the OLE migraine analysis set
Intercurrent Events	Rescue medication use: not applicable (rescue medication is part of the endpoint) Nonrescue acute headache medication use: not applicable (nonrescue acute headache medication is part of the endpoint) Prophylactic migraine medication use: treatment policy strategy Study drug discontinuation: treatment policy strategy
Objective 13	Proportion of subjects who use rescue medication after each of the first 5 qualifying migraine attacks during the OLE Phase
Efficacy Endpoint	Percentage of subjects who use rescue medication after each of the first 5 qualifying migraine attacks ≥ 23 hours apart in the OLE Phase
Summary	Percentage of subjects who have the event after each of the first 5 qualifying migraine attacks ≥ 23 hours apart in the OLE Phase by treatment group and overall for the OLE migraine analysis set
Intercurrent Events	Rescue medication use: not applicable (rescue medication is the endpoint) Nonrescue acute headache medication use: treatment policy strategy Prophylactic migraine medication use: treatment policy strategy Study drug discontinuation: treatment policy strategy
Objective 14	Frequencies of hepatic-related AEs and hepatic-related AEs leading to study drug discontinuation in subjects treated with rimegepant during the DBT and the OLE Phase
Safety Endpoint	Number and percentage of subjects with hepatic-related AEs and hepatic-related AEs leading to study drug discontinuation on treatment during the DBT Phase, and the OLE
Summary	Frequency (1) by treatment group on DBT for the DBT safety analysis set, and (2) treatment group and overall on OL rimegepant for the OL rimegepant safety analysis set
Intercurrent Events	Rescue medication use: treatment policy strategy Nonrescue acute headache medication use: treatment policy strategy Prophylactic migraine medication use: treatment policy strategy Study drug discontinuation: while-on-treatment strategy

Objective 15	Mean change from baseline in the MSQ restrictive role function domain score at Week 12 of the OLE Phase
Outcome Research Endpoint	Mean change from baseline in the MSQ restrictive role function domain score at Week 12 of the OLE Phase
Summary	Change from baseline using descriptive statistics by treatment group and overall for the OLE efficacy analysis set
Intercurrent Events	Rescue medication use: treatment policy strategy Nonrescue acute headache medication use: treatment policy strategy Prophylactic migraine medication use: treatment policy strategy Study drug discontinuation: treatment policy strategy
Objective 16	Frequency of LFT elevations based on fold changes above ULN in subjects treated with rimegepant during the DBT and OLE Phases
Safety Endpoint	Number and percentage of subjects with LFT elevations (ALT, AST, or TBL) based on fold changes above ULN on treatment during the DBT and OLE Phases
Summary	Frequency (1) by treatment group on DBT for the DBT safety analysis set with LFT data, and (2) treatment group and overall on OL rimegepant for the OL rimegepant safety analysis set with LFT data
Intercurrent Events	Rescue medication use: treatment policy strategy Nonrescue acute headache medication use: treatment policy strategy Prophylactic migraine medication use: treatment policy strategy Study drug discontinuation: while-on-treatment strategy
Objective 17	Primary and key secondary efficacy endpoints during the DBT Phase and high-level safety endpoints during the DBT and OLE Phases by history of clinically relevant CV disease (yes, no)
Efficacy and Safety Endpoints	
 Efficacy endpoints: see Table 1 and Table 2 Safety endpoints: see Table 3 Objective 4; also the number and percentage of subjects with AEs related to study drug by intensity on treatment during the DBT and OLE Phases
Summary	
 Efficacy endpoints: see Table 1 and Table 2 Safety endpoints: see Table 3 Objective 4
Intercurrent Events	
 Efficacy endpoints: see Table 1 and Table 2 Safety endpoints: see Table 3 Objective 4
Objective 18	Primary and key secondary efficacy endpoints during the DBT Phase by history of documented failure to ≥ 2 triptan medications with ≥ 1 failure due to lack of efficacy (yes, no)
Efficacy Endpoints	See Table 1 and Table 2.
Summary	See Table 1 and Table 2.
Intercurrent Events	See Table 1 and Table 2.

4 ANALYSIS SETS, TREATMENT GROUPS, AND SUBGROUPS

4.1 Analysis Sets

The following analysis sets are evaluated and used for presentation and analysis of the data:

- **Enrolled:** subjects who sign an informed consent form and are assigned a subject identification number, i.e., nonmissing informed consent date. This analysis set is used mainly to assess study population and in by-subject listings.
- **Full:** subjects in the enrolled analysis set who receive a randomized treatment group assignment (rimegepant or placebo) from RTSM, i.e., nonmissing RTSM randomization date. This analysis set is used mainly to assess study population.
 - **DBT efficacy:** subjects in the full analysis set who meet all the following criteria:
 - (1) Randomized only once
 - (2) Take double-blind (DB) study drug, i.e., nonmissing DB study drug date/time
 - (3) Have a qualifying migraine attack at the time of DB study drug dosing (see Section 6.3.5.5)
 - (4) Have DB postdose efficacy data. Defined as nonmissing efficacy data (i.e., nonmissing migraine headache pain intensity, phonophobia status, photophobia status, nausea status, or functional disability level) with eDiary measurement date in the DBT Phase analysis period at ≥ 1 planned time point postdose (i.e., 15 minutes through 48 hours).

This analysis set is used mainly to assess efficacy endpoints and MQoL in the DBT Phase.

- **OLE efficacy:** subjects in the DBT efficacy analysis set who take ≥ 1 dose of OL rimegepant, i.e., nonmissing OL rimegepant start date. This analysis set is used to assess outcomes research endpoints during the OLE Phase.
 - **OLE migraine:** subjects in the OLE efficacy analysis set with time in the OLE Phase ≥ 14 days. This analysis set is used to assess efficacy days in the OLE Phase.
- **Safety:** subjects in the enrolled analysis set who take ≥ 1 dose of study drug (DB rimegepant, DB placebo, or OL rimegepant). This analysis set is used to assess study population, exposure, and on-treatment safety.
 - **DBT safety:** subjects in the safety analysis set who take DB study drug. This analysis set is used to assess study population, exposure, and on-DBT safety.
 - **OL rimegepant safety:** subjects in the safety analysis set who take ≥ 1 dose of OL rimegepant, i.e., nonmissing OL rimegepant start date. This analysis set is used to assess study population, exposure, and on-OL rimegepant safety.

- Interim safety: subjects in the OL rimegepant safety analysis set with OL rimegepant start date – DB study drug date > 9 days. This analysis set is used to assess post-DBT pre-OL rimegepant safety.
- Follow-up safety: subjects in the safety analysis set whose last contact date is in the follow-up safety analysis period. This analysis set is used to assess follow-up safety.
- DB or OL rimegepant safety: subjects in the safety analysis set who take ≥ 1 dose of DB or OL rimegepant, i.e., nonmissing DB or OL rimegepant start date. This analysis set is used only to produce safety narrative subject identifiers.

See Section 7.1 for derived dates and 7.2 for analysis periods.

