9.2. Analysis Sets

- Enrolled: Subjects who sign informed consent and are assigned a subject identification number.
- Full: Subjects in the enrolled analysis set who receive a randomized treatment group assignment (rimegepant or placebo) from RTSM.
- DBT safety: Subjects in the enrolled analysis set who take double-blind study drug (rimegepant or placebo).

- OL rimegepant safety: Subjects in the enrolled analysis set who take ≥ 1 dose of OL rimegepant (75 mg ODT).
- DBT efficacy: Subjects in the full analysis set who: (1) are randomized only once; (2) take double-blind study drug; (3) have a qualifying migraine attack at the time of double-blind study drug dosing (see [Section 4.1](#)); and (4) have double-blind postdose efficacy data (i.e., nonmissing headache pain intensity, phonophobia status, photophobia status, nausea status, or functional disability level after taking double-blind study drug).
- OL rimegepant efficacy: Subjects in the DBT efficacy analysis set who take ≥ 1 dose of OL rimegepant (75 mg ODT).

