9.3.1.1. Primary Endpoint

Rimegepant will be tested for superiority against placebo at a 2-sided alpha level of 0.05 for the primary endpoint of migraine headache pain relief at 2 hours postdose during the DBT Phase using the DBT efficacy analysis set. Treatment groups will be compared using Mantel-Haenszel risk estimation with stratification by history of clinically relevant CV disease (yes, no), to estimate the difference in percentages of subjects achieving the endpoint response criteria (rimegepant – placebo). The percentage of subjects achieving the endpoint response criteria will be presented with a 95% confidence interval (CI) by treatment group. The

stratified difference in percentages between treatment groups will be presented with a 95% CI and p-value.

Subjects with missing data at 2 hours postdose will be classified as failures (i.e., Non-completer = Failure; NC=F).

Sensitivity analyses will be described in the SAP.

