6.3.1.2 Missing Efficacy Data During the DBT Phase

Missing efficacy data during the DBT Phase are tabulated by treatment group as the number and percentage of subjects in the DBT efficacy analysis set in the following categories:

- Missing headache pain intensity at each time point from 15 minutes through 48 hours postdose. These categories are not mutually exclusive because subjects may have missing headache pain intensity at multiple time points.
- Number of time points with missing migraine headache pain intensity from 2 hours to 48 hours postdose: 0 (i.e., no missing migraine headache pain intensity), 1, 2, 3, 4, 5, 6, 7. These categories are mutually exclusive.

- Missing data for the following efficacy parameters at 2, 24, and 48 hours postdose: migraine headache pain intensity, nausea status, phonophobia status, photophobia status, and functional disability level.

6.3.2 Primary Efficacy Endpoint: Pain Relief at 2 Hours Postdose During the DBT Phase

The primary efficacy endpoint is evaluated for the DBT efficacy analysis set.

Pain relief at a single time point postdose is defined as having a headache pain intensity of none or mild at that time point.

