- Other medication taken to treat headache or aura status (yes or no).
- Headache (Non-migraine) question category: headache (nonmigraine) characteristics parameters (OLE Phase only; see Section 7.4.3)
- MQoL question category: MQoL question parameters at 24 hours postdose (see Section 7.4.4)
- Manual DCF Study medication question category: manual DCF study medication date (see Section 7.4.1.2).

A set of eDiary parameters is defined as those with the same eDiary finding date/time and eDiary completion date/time. The eDiary finding date/time is an internal date/time that is derived by YPrime after the subject answers the first question in the set. The eDiary completion date/time is an internal date/time that is derived by YPrime after the subject answers the last question in the set and saves the results.

Refer to the latest versions of the YPrime C4951004 Data Transfer Specification and eCOA System Requirements Document for additional details.

7.4.1 eDiary Study Medication

7.4.1.1 eDiary Reported Study Medication Date/time

The raw eDiary dataset has a reported study medication date/time parameter (DOSDATIM) with a value that is derived by YPrime from data entered by subjects in study medication parameters the Migraine question category. Date and time are both nonmissing.

Each distinct reported study medication date/time is derived from a distinct set of Migraine question category parameters at the time of prospective or retrospective study drug dosing.

A set of Migraine question category parameters at the time of prospective study drug dosing is defined as one in which (1) there is a “no” response to the eDiary question about already taking study medication, and (2) there is a “yes” response to the eDiary question about confirming that study medication was taken, and (3) eDiary planned time point is missing. The reported study medication date/time is derived by YPrime as the eDiary completion date/time.

A set of Migraine question category parameters at the time of retrospective study drug dosing is defined as one in which (1) there is a “yes” response to the eDiary question about already taking study medication, and (2) eDiary planned time point is missing. Subjects may enter study medication parameters retrospectively on or 1 day before the eDiary finding date as follows:

- During the DBT Phase, subjects must first report taking study medication either “today” or “other”.

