9.3 Analyses of Reliability of Rimegepant Effect in the OLE Phase

9.3.1 EQMAs

A qualifying migraine attack is defined as an attack of moderate or severe migraine headache pain intensity that is first treated with study drug. Each qualifying migraine attack is derived from a distinct set of Migraine question category parameters at the time of study drug dosing that has both of the following parameter values in the same set:

- 1) Migraine headache pain intensity of moderate or severe
- 2) Other medication taken to treat headache or aura status of “no”.

The set of Migraine question category parameters at the time of study drug dosing is linked to an eDiary reported study medication date/time (see Sections 7.4 and 7.4.1.1).

An EQMA is defined as a qualifying migraine attack in the appropriate phase analysis period (DBT or OLE) with a nonmissing MQoL Question 16 value at 24 hours postdose in the appropriate outcomes research analysis period (DBT or OLE). The eDiary measurement date/time for a given qualifying migraine attack is the eDiary reported study medication

date/time to which it is linked, and is used to determine whether there is a nonmissing MQoL Question 16 value in the corresponding 24-hour analysis window (see Section 7.4.4) in the outcomes research analysis period. If a subject has >1 MQoL set in the same analysis window, then the MQoL set with the earliest eDiary finding date/time and nonmissing MQoL Question 16 value in the outcomes research analysis period is selected for that qualifying migraine attack.

During the OLE Phase, the first 5 EQMAs $\geq X$ hours apart in the OLE Phase are identified as follows:

- 1) All EQMAs during the OLE Phase are sorted by the (1) eDiary measurement date (ignoring time), and (2) eDiary finding date/time.
- 2) If a subject has >1 EQMA on the same eDiary measurement date, then the EQMA with the earliest eDiary finding date/time is selected.
- 3) The first 5 EQMAs $\geq X$ hours apart in the OLE Phase are selected based on the first 5 eDiary measurement date/times being $\geq X$ hours apart.
 - $X = 23$ in the main analysis, whereas $X = 47$ in the sensitivity analysis (see Section 6.5.1.1). The cutoffs of 23 and 47 hours align with the lower bounds of the 24-hour and 48-hour postdose analysis windows, respectively (see Table 7).
 - The first EQMA is included in both analyses, and is the starting point.

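### The primary analysis set drops randomised, dosed subjects who record nothing after dosing, and no planned sensitivity analysis restores them

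*SAP*

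**What the plan says.** SAP 6.3.2 states: "The primary efficacy endpoint is evaluated for the DBT efficacy analysis set". SAP 4.1 sets four conditions for that set: randomised once, double-blind drug taken, a qualifying attack at dosing, and "Have DB postdose efficacy data", meaning a nonmissing value of any efficacy parameter at one or more planned time points from 15 minutes to 48 hours. Protocol 9.2 has the same fourth condition: "have double-blind postdose efficacy data (i.e., nonmissing headache pain intensity", or any of the other four parameters.

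Inside the set, Protocol 9.3.1.1 is strict: "Subjects with missing data at 2 hours postdose will be classified as failures". SAP 6.3 makes this rule (NC=F) the main method for single-time-point endpoints.

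SAP 6.3.2.2 plans two sensitivity analyses, copy reference multiple imputation and imputation at response rates of 0% to 30%. Each repeats the main analysis and changes only how a missing 2-hour value is filled. Of the full analysis set, SAP 4.1 says "This analysis set is used mainly to assess study population".

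For the third condition, SAP 9.3.1 derives a qualifying attack from the eDiary dosing set: pain moderate or severe, and "Other medication taken to treat headache or aura status of" no. SAP 7.4.1.1 allows that set to be completed after the dose: "Subjects may enter study medication parameters retrospectively on or 1 day before the eDiary finding date as follows".

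**The concern.** Criterion 4 makes membership of the primary analysis set depend on what a subject does after dosing. It also treats the more complete non-response more leniently: one 15-minute entry and nothing more is a failure, while no entry at all is an exclusion. If the chance of recording nothing differs between arms, the comparison is no longer between the groups as randomised and dosed. The same set serves the key secondary endpoints.

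Criterion 3 raises a lesser question. It describes status at dosing, but when the dosing entry is retrospective the pain and other-medication answers are given after the dose. In addition, a dose known only from a manual data correction form has no linked eDiary dosing set (SAP 7.4.1.2 and 9.3.1). Such a subject cannot meet criterion 3, whatever the attack was like.

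**Working it through.** **Inputs.** Response rates of 57.9% (rimegepant) and 43.9% (placebo), 270 evaluable per arm, two-sided alpha 0.05 and about 90% power come from Protocol 9.1 and SAP 5. The number of dosed subjects excluded under criterion 4 is not given. Every count k below is an assumption, with range 0 to 30 per arm.

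**1. The plan's own figure.** Power = Φ[(p1 − p2 − 1.96·s0)/s1], with s0 the pooled and s1 the unpooled standard error. At 270 per arm, s0 = 0.0430 and s1 = 0.0426, so power = Φ[(0.140 − 1.96 × 0.0430)/0.0426] = 90.4%. The stated 90% is reproduced. Also, 300 × 0.90 = 270, so the whole 10% loss is put down to having no migraine. Nothing is allowed for dosed subjects without data.

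**2. Restoring excluded subjects as failures.** Expected responders stay at 0.579 × 270 = 156.3 and 0.439 × 270 = 118.5; only the denominators grow. The difference is 156.3/(270 + k_R) − 118.5/(270 + k_P).

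| Restored, rimegepant / placebo | Rates | Difference (points) | Power |
|---|---|---|---|
| 0 / 0 | 57.9% / 43.9% | 14.0 | 90.4% |
| 8 / 8 | 156.3/278 = 56.2%; 118.5/278 = 42.6% | 13.6 | 89.6% |
| 30 / 30 | 156.3/300 = 52.1%; 118.5/300 = 39.5% | 12.6 | 87.4% |
| 8 / 2 | 156.3/278 = 56.2%; 118.5/272 = 43.6% | 12.7 | 84.5% |
| 2 / 8 | 156.3/272 = 57.5%; 118.5/278 = 42.6% | 14.8 | 93.8% |
| 14 / 0 | 156.3/284 = 55.0%; 43.9% | 11.1 | 74.8% |
| 0 / 14 | 57.9%; 118.5/284 = 41.7% | 16.2 | 96.9% |

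Equal losses barely matter. Unequal losses move the difference in either direction.

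**3. Near the significance boundary.** This uses an unstratified risk-difference z test with unpooled standard error and placebo fixed at 119/270. The smallest significant rimegepant result is 142/270: difference 8.5 points, SE 4.29, p = 0.047. One restored rimegepant failure (142/271) gives 8.3 points and p = 0.052. At 145/270 it takes 7 restored failures to lose significance, at 148/270 it takes 13, and at 156/270 (13.7 points, close to the planned effect) it takes 29.

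**4. Where the excluded subjects appear.** Analysis-set counts by arm are in SAP 6.2.1. Dosing without a qualifying attack is tabulated in SAP 6.2.6.2 and again as a deviation under 9.1. A by-subject listing with the reason for exclusion is in SAP 6.3.1.1. The missing-data table (SAP 6.3.1.2) covers only the DBT efficacy set, so it cannot count subjects removed by criterion 4. None of these outputs gives a treatment difference with the subjects included.

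**The case against.** Criterion 4 is lenient. One value of any of five parameters at any of twelve time points keeps a subject in, so only those with no postdose data at all are lost, and they may be few. The outputs in step 4 would reveal an imbalance. Both arguments stand. They limit the size of the problem, but they do not show what the exclusions do to the estimate.

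Three stronger readings are tempting, and the documents do not support them.

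- A reader might infer that NC=F already requires these subjects to be analysed. It does not. NC=F scores a missing time point for subjects who are in the set; it does not decide who is in it.
- A reader might infer that early relief or rescue use disqualifies retrospective reporters under criterion 3. That depends on whether the eDiary asks about the time of dosing or the time of entry. SAP 7.4 leaves such detail to the eDiary vendor's specification documents. The planned route is prospective in any case: Protocol 4.3.2 and Table 1 have the drug taken only after the pre-dose assessments. That the most-bothersome-symptom item is collected only before dosing (SAP 7.4.2) does not settle how the other items are worded.
- A reader might infer that the exclusions favour rimegepant. No direction is documented, and exclusions linked to rescue use could plausibly fall more on placebo.

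**Conclusion.** The point holds in a narrow form. Criterion 4 removes randomised subjects who dosed for a qualifying attack because they recorded nothing afterwards, and neither planned sensitivity analysis puts them back. For criterion 3, dependence on answers given after dosing is possible for retrospective entries but not shown.

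The size is unknown. If 270 per arm respond at the planned rates and restored subjects count as failures, balanced exclusions of up to 30 per arm leave at least 12.6 points and 87.4% power. The finding is material only if exclusions differ by arm (14 in rimegepant alone would give 11.1 points) or if the observed result is close to the boundary. It is a cheap improvement, with no need to change the primary analysis.

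**What to change.** Add one sensitivity analysis of the primary endpoint to SAP 6.3.2.2. The population is all subjects randomised once who took double-blind study drug for a qualifying attack, regardless of criterion 4. Apply NC=F and RM=F, so that a subject with no postdose data is a failure.

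Tabulate exclusions under criteria 3 and 4 by arm, separating prospective, retrospective and manual-correction-form dosing entries.

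As a supplementary row, add dosed subjects excluded under criterion 3 because of a retrospective entry. Use their observed 2-hour value where there is one, and score failure only if it is missing or rescue was taken. Scoring all of them as failures would overwrite observed responses.

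Do not re-judge prior medication from the CRFs. SAP 6.2.6.3 documents clock time for rescue medications, but no clock time is documented for concomitant medications, so same-day use may not be orderable against the dose.

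The cost is one extra table with its counts, and slightly diluted response rates in that table. Exclusion reasons are already derived for the listing in SAP 6.3.1.1, and Protocol 9.3.1.1 leaves sensitivity analyses to the SAP. The addition should be specified before unblinding.
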